# 5.4. Timing of Analysis

The final analysis for the primary objective will be performed when majority of patients responding to futibatinib had at least 6 months of follow-up from onset of response.

#### 6. STATISTICAL ANALYSIS

#### 6.1. General Methods

All relevant data will be presented in patient level data listings.

All categorical (binary and ordinal) data will be summarized using frequency counts and percentages of patients. Percentage will be calculated using the corresponding treatment group in the study population as the denominator. The continuous variables will be summarized using number of non-missing observation (n), mean, standard deviation (SD), median, minimum and maximum unless otherwise specified. The number of events and censorings will be reported for time-to-event analysis. All estimations will include a point estimate and the corresponding 95% confidence interval.

The recommended phase 2 dose (RP2D) is 20 mg daily (QD). The treatment dose level is 20 mg during the regular treatment in Phase 2 of the study.

A formal interim analysis, as well as interim analysis for safety will be performed in this Phase 2 part of the study (Section 6.8).

For concomitant medications/therapy and adverse events, the cycles are determined based on their start/onset dates. For other collected data, the cycles are determined based on their visit dates. These data include Lab test, Physical exam, Vital signs, Height and weight, Ophthalmological exam, Neurological exam, ECOG, ECG, Pregnancy test, PK, ctDNA, PRO data, Scheduled tumor assessment.

When there are multiple laboratory records for a scheduled visit, the one closest to the target date (relative to the Day 1 in that cycle) will be used for analysis. If there are two or more records with the same time period to the target date, the later one will be used for analysis.

Time to event distribution (e.g. progression free survival, overall survival, time to response, and duration of response) will be estimated using Kaplan Meier techniques. When appropriate, the median along with the corresponding log-log transformed 95% CI will be estimated. Rates at fixed time points will be derived from the Kaplan Meier estimate and corresponding confidence interval will be derived based on Greenwood formula for variance derivation and on log-log transformation applied on the survivor function S(t). Confidence intervals for binomial proportions, ORR and DCR, will be derived using the Clopper-Pearson method.

All the analyses of efficacy, safety, and pharmacodynamics data for this study will be performed using SAS® statistical software package, Version 9.3 or a later version.

# 6.2. Study Conduct

#### 6.2.1. Accrual

The accrual will be summarized on the enrolled population separately with number of patients accrued by country and investigational site.

A patient level listing of accrual will also be produced.

#### **6.2.2.** Protocol Deviations

Important protocol deviation (ICH E3 Q&A (R1)) is defined as a subset of protocol deviations that may significantly impact the completeness, accuracy, and/or reliability of the study data or that may significantly affect the subject's rights, safety or well-being. These include: Important ICF issues, inclusion/exclusion criteria not met, withdrawal criteria not followed; wrong treatment, incorrect dose/overdose based on protocol definitions, important deviations based on protocol design, and other important GCP deviations.

Important protocol deviations will be summarized and listed in the Clinical Study Report (CSR).

Relevant protocol deviations are a subset of important protocol deviations that may impact study endpoints. Relevant protocol deviation in phase 2 of this study includes patients who do not have evaluable post-baseline tumor assessment.

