# **5.3.** Populations for Analysis

- **Safety Population:** All patients who received at least 1 dose of TAS-120. This population will be the primary population for safety evaluation
- Efficacy Population: All Intra-hepatic cholangiocarcinoma (iCCA) patients who received at least 1 dose of TAS-120 with FGFR2 gene fusions or other FGFR2 rearrangements
- PRO Population: All patients who received TAS-120 treatment and had EQ-5D or EORTC QLQ-C30 assessment at baseline and at least one subsequent post-baseline assessment
- Per-protocol Patients (Per-Protocol Population): All treated subjects who have no relevant protocol deviations. For patients who have a relevant deviation during the study, data collected before the point of deviation can be included in the analysis preformed for this population.

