# **6.4.** Efficacy Analyses

#### 6.4.1. Primary Efficacy Analyses

The primary endpoint, Objective Response Rate (ORR), defined as the proportion of patients who achieved best overall response of partial response (PR) or complete response (CR) per RECIST 1.1 based on Independent Review Committee (IRC) in the Efficacy Population, will be summarized by a binomial response rate. ORR will be calculated from the best of overall response recorded from the start of treatment until progression disease or start of subsequent new anticancer treatment. The overall response can be derived based on target lesion response, non-target response as well as the emergence of new lesion for patients with measurable disease at baseline. Table 4 presents the rules to derive the overall response.

The best overall response, CR and PR, will be confirmed with at least 4 weeks intervals of two consecutive time points. A minimum of 6-week interval between initial of treatment (first dose date) and tumor measurement is required for SD. The confirmation rule of the best of overall response is shown in Table 5.

95% confidence interval (binomial proportion confidence interval) for ORR will be constructed with Clopper-Pearson 95% CI. The null hypothesis will be rejected if the 2-sided 95% CI lower

bound is greater than 10%. This translates in observing at least 17 responders out of 100 in the Efficacy Population.

The objective response rate will be created by both independent review and investigator review. The primary endpoints, ORR, assessed with RECIST 1.1, will be displayed in the efficacy tables with both independent and investigator review.

Table 4. Overall Response Assessment with Target/Non-target Lesion and New Lesions

Target Lesions	Non-target Lesions	New Lesions	Overall Response
CR	CR	No	CR
CR	Non-CR/Non-PD or Not all evaluated	No	PR
PR	Non-PD or Not all evaluated	No	PR
SD	Non-PD or Not all evaluated	No	SD
Not all evaluated	Non-PD	No	Not evaluable
PD	Any	Yes or No	PD
Any	PD	Yes or No	PD
Any	Any	Yes	PD

Table 5. Confirmation Rules for Overall Response of PR and CR

Earlier Response	Later Response	Confirmed Response
(to be confirmed)	(confirmation)	
CR	CR	CR
CR	Not CR or missing	SD
PR	CR or PR	PR
PR	SD or PD or missing	SD
PR	SD and then PR (only one SD in between)	PR
SD	n/a – no confirmation needed	SD
PD	n/a – no confirmation needed	PD

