# **6.4.2.1.** Sensitivity Analyses

The following sensitivity analyses will be performed on the key efficacy endpoints as follows:

- Primary efficacy endpoint (ORR) based on the Per-protocol Analysis Set using a similar analysis method as the primary analysis
- ORR and PFS based on assessments by the investigator or local radiologist on the Efficacy Population

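### The only relevant deviation the Phase 2 SAP names removes non-responders alone from the Per-Protocol ORR, and no eligibility breach is designated as relevant

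*SAP*

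**What the plan says.** Phase 2 SAP 5.3 defines the Per-Protocol set as "All treated subjects who have no relevant protocol deviations". For a patient with such a deviation it adds that "data collected before the point of deviation can be included in the analysis preformed for this population". The Efficacy Population, which is the primary denominator, is defined in the same section as iCCA "patients who received at least 1 dose of TAS-120 with FGFR2 gene fusions or other FGFR2 rearrangements"; it requires no post-baseline scan.

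Section 6.2.2 sets up two tiers. Important deviations come first: "These include: Important ICF issues, inclusion/exclusion criteria not met, withdrawal criteria not followed", followed by treatment and dosing errors and other items. Then: "Relevant protocol deviations are a subset of important protocol deviations that may impact study endpoints". The only instance given is: "Relevant protocol deviation in phase 2 of this study includes patients who do not have evaluable post-baseline tumor assessment".

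Section 6.4.2.1 lists two sensitivity analyses. One is "Primary efficacy endpoint (ORR) based on the Per-protocol Analysis Set using a similar analysis method as the primary analysis". The other repeats ORR and PFS with investigator or local assessments in the Efficacy Population, so it changes the reader and not the patients.

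On response, 6.4.1 states: "The best overall response, CR and PR, will be confirmed with at least 4 weeks intervals of two consecutive time points". Table 5 of that section downgrades a PR or CR with no later confirming assessment to SD.

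**The concern.** A Per-Protocol analysis should show whether the result depends on patients who were outside the intended population or were not treated as planned. The one exclusion named here does not do that.

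A patient can lack an evaluable post-baseline scan and have broken no rule. Under protocol 9.17.1 the first scan is due at the end of Cycle 2 (day 42), up to two weeks late. An end-of-treatment scan is required only if the previous scan was at least 9 weeks before discontinuation. Take a patient scanned 2 weeks before the first dose who stops for clinical deterioration at week 5. That is 7 weeks since the last scan, so no end-of-treatment scan is required. If the patient then dies or starts other therapy before the next scan is due, there is no post-baseline scan and no breach. Yet 6.2.2 places the patient within a subset of protocol deviations.

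The eligibility breaches that could bear on ORR are not designated as relevant: no prior gemcitabine-platinum (inclusion 3b(ii)), no documented radiologic progression (3b(iii)) and prior FGFR-directed therapy (exclusion 6f). At stake is how much weight the Per-Protocol ORR can carry as support for the primary result.

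**Working it through.** **Inputs.** N = 100, null ORR 10%, two-sided 95% Clopper-Pearson interval, threshold 17 responders (Phase 2 SAP 6.4.1). The number k without an evaluable post-baseline scan is not given; 2 to 15 of 100 is assumed. The number of ineligible patients is also an assumption.

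**Step 1: the SAP's own figure.** The lower limit for x of n is the 0.025 quantile of Beta(x, n-x+1).

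- 16/100: 9.43%, not above 10%.
- 17/100: 10.23%, above 10%.

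The stated threshold of 17 is reproduced.

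**Step 2: the named exclusion.** A confirmed CR or PR needs two post-baseline time points. A patient with no evaluable one therefore counts in n and never in x. Removing k such patients gives x/(100-k), which is the primary ORR multiplied by 100/(100-k).

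| k removed | factor | 17 responders (lower limit) | 30 responders | 40 responders |
|---|---|---|---|---|
| 0 | 1.00 | 17.0% (10.23%) | 30.0% | 40.0% |
| 2 | 1.02 | 17.3% (10.44%) | 30.6% | 40.8% |
| 5 | 1.05 | 17.9% (10.78%) | 31.6% | 42.1% |
| 10 | 1.11 | 18.9% (11.41%) | 33.3% | 44.4% |
| 15 | 1.18 | 20.0% (12.10%) | 35.3% | 47.1% |

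The factor is never below 1.

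**Step 3: an eligibility-based exclusion, for contrast.** Remove m ineligible patients, j of them responders, and keep unscanned patients in the denominator. The ORR becomes (x-j)/(100-m), which is lower than x/100 whenever j/m exceeds x/100. With x = 17 and m = 5:

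- j = 0: 17/95 = 17.9%, lower limit 10.78%
- j = 1: 16/95 = 16.8%, lower limit 9.94%
- j = 2: 15/95 = 15.8%, lower limit 9.12%
- j = 5: 12/95 = 12.6%, lower limit 6.70%

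This set can move either way, so it can contradict the primary result as well as support it.

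**Step 4: nesting.** Section 5.3 draws the Per-Protocol set from all treated subjects and does not say it lies within the Efficacy Population. If three treated non-responders from outside that population entered, 17/100 would become 17/103 = 16.5%, lower limit 9.92%.

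**The case against.** A reader might infer that the Per-Protocol ORR can only rise, and that ineligible patients stay in the set. The text does not support either. The verb in 6.2.2 is *includes*, so the list is not closed, and the parent class expressly contains unmet eligibility criteria. An eligibility breach that affects ORR fits the definition of a relevant deviation, and if such breaches were applied the ORR could fall. Step 4 shows a second way it could fall. What stands is narrower: the only named item cannot lower the ORR within the Efficacy Population, and whether any eligibility breach counts is unspecified. In an open-label single-arm study, an open list leaves those exclusions to be settled when responses may already be known.

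A reader might also infer that the exclusion could rescue a failed trial, since 16/100 (lower limit 9.43%) becomes 16/94 = 17.0% (lower limit 10.05%) if six patients are dropped. It could not. Section 6.4.1 ties the 10% rule to the Efficacy Population, and nothing lets the Per-Protocol result override it.

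Three further points carry some weight.

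- A missing scan can be a real conduct deviation. The protocol schedules scans, and patients who stop for reasons other than radiologic progression should continue them until progression or new therapy. So the named group is mixed, but the SAP does not separate missed scans from early deaths.
- Excluding patients without measurable disease (inclusion 4) would itself remove mostly non-responders. Protocol Table 14 offers no PR to patients with only non-target disease.
- Important deviations will be summarised and listed (6.2.2), population sizes and exclusion reasons tabulated (6.3.1), and ORR shown by number of prior lines and by FGFR testing status (6.4.3). A reader could identify ineligible patients from these, but none gives an ORR without them.

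**Conclusion.** The point holds in this form: the one relevant deviation named in 6.2.2 is often an outcome, it selects only primary-analysis non-responders, and no eligibility breach is designated as relevant. Applied alone within the Efficacy Population, it leaves the ORR unchanged at k = 0 and otherwise raises it. With an assumed 5 to 10 of 100 removed, the rise is from 40.0% to between 42.1% and 44.4%, or from 17.0% to between 17.9% and 18.9%. The direction follows from the confirmation rule and needs no assumption about k. It does assume that evaluability is judged by the same independent review as the primary ORR, which 6.2.2 does not state.

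The primary analysis and the 17-in-100 rule are unaffected. This is a weakness in a supporting analysis; it should be corrected, but it does not threaten the main conclusion.

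**What to change.** In Phase 2 SAP 6.2.2 and 5.3:

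1. Delete the absence of an evaluable post-baseline tumor assessment as a relevant deviation.
2. Define the Per-Protocol set as a subset of the Efficacy Population, and keep unscanned patients in its denominator as non-responders.
3. Replace the open wording with a closed list, fixed before database lock, of breaches determined at baseline: no prior gemcitabine-platinum, no documented radiologic progression, prior FGFR-directed therapy. If absence of measurable disease is added, note that it removes mostly patients who cannot have a PR.
4. State that the rule retaining data from before the deviation does not apply to ORR. It has no clear meaning for a patient with no evaluable post-baseline scan, and a baseline breach precedes all response data.
5. If a scan-based figure is wanted, report it separately as a response-evaluable ORR.

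The cost is mainly SAP wording. Unmet eligibility criteria are already classed as important deviations and prior systemic therapies are to be listed, but no case report form is available to confirm that every item is recorded in usable form. The Per-Protocol ORR would lose the upward shift from dropping unscanned patients, and the eligibility exclusions could move it either way.

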# 6.3. Study Population

# **6.3.1.** Patient Disposition

The number of patients in each study population will be summarized in a table with 5 major analysis sets, safety population, efficacy population, per-protocol population, PK population, and PRO population. Patient disposition table will include number of patients treated at data cutoff, number of discontinued patients along with the reason for exclusion from the population. In addition, patients' status with regard to study treatment and follow-up will also be summarized, along with the reasons for study discontinuations.

### **6.3.2.** Demographic and Other Baseline Characteristics

The following baseline characteristics will be summarized. Listings will also be provided:

- Age (descriptive statistics)
- Age category (<65, >=65)
- Gender (male, female)
- Race groups (Caucasian/white, Black, Asian/Oriental, American Indian or Alaska Native, Native Hawaiian or Other Pacific Islander, Other)
- Regions (North America, Europe, Asia Pacific(excluding Japan), Japan)
- Ethnicity (Hispanic/latino, Not Hispanic/Latino)
- ECOG Performance Status (1, 0)
- Baseline Weight (kg)
- Baseline Height (cm)
- Baseline *FGFR* rearrangements status by local lab (commercial test provided to clinician as standard of care based on tumor tissue) and/or central lab (clinical trial assay performed on tumor tissue)
- Prior surgical resection of primary tumor (Yes/No)

• Prior (neo) adjuvant treatment (Yes, No)

FGFR2 aberration types will be summarized. A patient level listing will also be provided.

Pre-study anti-cancer surgery and prior radiation therapy will be summarized. For prior-radiation therapy, the number and percentage of patients with palliative and therapeutic radiation therapies will be presented in a summary table.

All prior systemic anticancer therapies (adjuvant therapies, neoadjuvant therapies, therapies for advanced/metastatic disease, and maintenance therapies) will be summarized. The number of patients with 1, 2, and >=3 prior regimens will be summarized for all systemic anticancer therapies and for advanced/metastatic disease only.

All collected information for cancer diagnosis, pre-study surgery, prior-radiation therapy, and prior systemic anti-cancer therapy will be summarized and listed.

#### 6.3.3. Medical History

Medical history will be coded according to the Medical Dictionary for Regulatory Activities (MedDRA 22.0). Medical history will be listed by patient number, start date and end date. The treatment start date and end date versus the first dose date maybe listed.

### 6.3.4. Prior/Concomitant Therapy and Therapies

Prior or concomitant medications and therapies will be collected from the time of informed consent through 30 days after administration of last dose of study medication.

Medications and therapies which started and stopped prior to the first dose of TAS-120 are considered as prior medications. Medications and therapies which started prior to the first dose of TAS-120 and continued into the treatment period are considered as prior and concomitant medications and therapies.

Medications or therapies with a start date from first dose of TAS-120 to 30 days after administration of the last dose of TAS-120 will be considered as concomitant medications or therapies.

Prior and concomitant medications will be coded according to World Health Organization (WHO) Drug Dictionary for Concomitant Medication. The concomitant medications will be summarized by ATC level 2 (Therapeutic Main Group) and ATC level 4 (Chemical/Therapeutic Subgroup) using the number and percentage of patients. Medications will be sorted in descending order of frequency of ATC level 2 and ATC level 4 within ATC level 2 in the total column. A patient will be counted only once within each level of summation if the patient has taken a medication more than once.

All prior and concomitant medications and therapies will be listed.

### **6.3.4.1.** Prior Anticancer Therapy

Pre-study anti-cancer surgery and prior radiation therapy will be summarized. For pre-study surgery, the number and percentage of patients with biopsy, primary tumor removal, metastatic tumor removal will be reported. For prior-radiation therapy, the number and percentage of patients with palliative and therapeutic radiation therapies will be presented in a summary table.

All prior systemic anticancer therapies (adjuvant therapies, neoadjuvant therapies, therapies for advanced/metastatic disease, and maintenance therapies) will be summarized. The number of patients with 1, 2 and >=3 prior regimens will be summarized for all systemic anticancer therapies and for advanced/metastatic disease only. The number of patients and percent with best of response for prior systemic anticancer therapy will also be summarized.

All collected information for cancer diagnosis, pre-study surgery, prior-radiation therapy, and prior systemic anti-cancer therapy will be summarized and listed.

# 6.3.4.2. Other Prior/Concomitant Therapy

Prior/current medication will be classified by anatomic and therapeutic classes. Agents and medication will be reported using the generic name. A listing by patient will also be provided.

In addition, percentage of subjects who received concomitant medication for management of hyperphosphatemia will be reported by cohort (percentages of treated subjects by medication class and generic term).

Total duration of medications (excluding overlaps) given for management of hyperphosphatemia will be also summarized.

# **6.4.** Efficacy Analyses

#### 6.4.1. Primary Efficacy Analyses

The primary endpoint, Objective Response Rate (ORR), defined as the proportion of patients who achieved best overall response of partial response (PR) or complete response (CR) per RECIST 1.1 based on Independent Review Committee (IRC) in the Efficacy Population, will be summarized by a binomial response rate. ORR will be calculated from the best of overall response recorded from the start of treatment until progression disease or start of subsequent new anticancer treatment. The overall response can be derived based on target lesion response, non-target response as well as the emergence of new lesion for patients with measurable disease at baseline. Table 4 presents the rules to derive the overall response.

The best overall response, CR and PR, will be confirmed with at least 4 weeks intervals of two consecutive time points. A minimum of 6-week interval between initial of treatment (first dose date) and tumor measurement is required for SD. The confirmation rule of the best of overall response is shown in Table 5.

95% confidence interval (binomial proportion confidence interval) for ORR will be constructed with Clopper-Pearson 95% CI. The null hypothesis will be rejected if the 2-sided 95% CI lower

bound is greater than 10%. This translates in observing at least 17 responders out of 100 in the Efficacy Population.

The objective response rate will be created by both independent review and investigator review. The primary endpoints, ORR, assessed with RECIST 1.1, will be displayed in the efficacy tables with both independent and investigator review.

Table 4. Overall Response Assessment with Target/Non-target Lesion and New Lesions

Target Lesions	Non-target Lesions	New Lesions	Overall Response
CR	CR	No	CR
CR	Non-CR/Non-PD or Not all evaluated	No	PR
PR	Non-PD or Not all evaluated	No	PR
SD	Non-PD or Not all evaluated	No	SD
Not all evaluated	Non-PD	No	Not evaluable
PD	Any	Yes or No	PD
Any	PD	Yes or No	PD
Any	Any	Yes	PD

Table 5. Confirmation Rules for Overall Response of PR and CR

Earlier Response	Later Response	Confirmed Response
(to be confirmed)	(confirmation)	
CR	CR	CR
CR	Not CR or missing	SD
PR	CR or PR	PR
PR	SD or PD or missing	SD
PR	SD and then PR (only one SD in between)	PR
SD	n/a – no confirmation needed	SD
PD	n/a – no confirmation needed	PD

